- Peripheral eosinophilia ($\geq 4\%$), from chart review

7. Lower prevalence of food allergy, measured as

- a) the proportion with parental report of provider diagnosis, defined as a "yes" response to this question derived from the National Health Interview Survey¹⁰:

Has your child ever been diagnosed with a food allergy by a health care provider?

- b) Parental report of a provider diagnosis of food allergy that was confirmed by prick testing or IgE blood test, defined as "yes" to both the previous question and this one:

Did your child have a positive test to any of the above foods using a skin prick test or blood test?

- c) Parental report of immediate food allergy symptoms: a "yes" response to

Has your child ever had an allergic reaction within 2 hours of eating a food? (i.e. swelling of the face or lips, red rash, hives, stomach pain, vomiting, or wheezing/difficulty breathing)?

d) All three (3) of the above criteria, which may be described as near definite food allergy.

8. Lower prescription (Y/N) topical medication use or over-the-counter hydrocortisone usage in (1) all children and (2) those with AD only.

a) Parent reported prescription topical medications, defined as either or both of the following responses to this question:

Have you treated the red rash or eczema with any of the following? (check all that apply)

Prescription steroid/cortisone cream/ointment from a healthcare provider (example, hydrocortisone 2.5% or triamcinolone cream or ointment)

Prescription non-steroidal cream/ointment (example: Protopic, tacrolimus, Elidel, Eucrisa)

b) Parent-reported prescription or over-the-counter topical medications, defined as the prescriptions above *or*:

Hydrocortisone cream that you can buy without a prescription

Other anti-itch cream that you can buy without a prescription

c) Therapy(ies) recorded in chart; see definition for CS-2 above for description of prescription and over-the-counter therapies.

9. Lower severity of AD symptoms in intervention vs control *cases* as reflected by

a) Lower mean Patient-Oriented Eczema Measure (POEM), a validated symptom index that includes sleep and itch¹¹. Each of the questions has the possible responses of (0, No days | 1, 1-2 days | 2, 3-4 days | 3, 5-6 days | 4, Every day). To score, calculate the sum of the seven items for any respondent who answered at least five of the component questions (if the incomplete responses are <10% of the total responses).

Over the last week, on how many days [nights, item 2] has your child's ...

... skin been itchy because of their eczema?

... sleep been disturbed because of their eczema?

... skin been bleeding because of their eczema?

... skin been weeping or oozing clear fluid because of their eczema?

... skin been cracked because of their eczema?

... skin been flaking off because of their eczema?

... skin felt dry or rough because of their eczema?

b) Lower mean score on the 30-point Infants' Dermatitis Quality of Life Index (IDQOL) where higher scores indicate more impairment¹². To score, sum the items below. A missing item will result in a missing response.

Over the last week, HOW SEVERE do you think your child's dermatitis has been? In other words, how red, scaly, inflamed or widespread.

4, Extremely Severe | 3, Severe | 2, Average | 1, Fairly Good | 0, No Eczema

Over the last week, how much has your child been ITCHING AND SCRATCHING?

3, All the time | 2, A lot | 1, A little | 0, None

Over the last week, what has your child's MOOD been?

3, Always crying, extremely difficult | 2, Very fretful | 1, Slightly fretful | 0, Happy

How many nights in the past week would you say your child's sleep was disturbed at night, not including routine feeding? 0-7

Over the last week approximately how much TIME on average has it taken TO GET your child OFF TO SLEEP each night?

3, More than 2 hours | 2, 1 to 2 hours | 1, 15 minutes to 1 hour | 0, 0 to 15 minutes

Over the last week, what was the TOTAL TIME that your child's SLEEP WAS DISTURBED on average each night?

3, 5 hours or more | 2, 3-4 hours | 1, 1-2 hours | 0, Less than 1 hour

Over the last week, has your child's eczema interfered with PLAYING OR SWIMMING?

3, Very much | 2, A lot | 1, A little | 0, Not at all

Over the last week, has your child's eczema interfered with them TAKING PART IN or ENJOYING OTHER FAMILY ACTIVITIES?

3, Very much | 2, A lot | 1, A little | 0, Not at all

Over the last week, have there been problems with your child at MEALTIMES because of the eczema?

3, Very much | 2, A lot | 1, A little | 0, Not at all

Over the last week, have there been problems with your child caused by the TREATMENT?

3, Very much | 2, A lot | 1, A little | 0, Not at all

Over the last week, has your child's eczema meant that DRESSING AND UNDRESSING the child has been UNCOMFORTABLE?

3, Very much | 2, A lot | 1, A little | 0, Not at all

Over the last week, how much has your child having eczema been a problem at BATH TIME?

3, Very much | 2, A lot | 1, A little | 0, Not at all

10. Delayed onset of AD, with age of onset determined by

a) provider-recorded date of first diagnosis retrieved from record review of chart by research coordinator

[Field:] Date (or age of child in months) of first AD diagnosis in the chart

b) parental report of eczema age of onset to the nearest 3 months (based on quarterly contacts)

Note: For interval-censored analysis, these variables will use the date of visit/response and previous visit/response as the end and start of the interval, respectively.

11. Lower mean days of disrupted sleep in the past week for infants reported by parents at 12 and 24 months, taken from the single item (#4) in the IDQoL.

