- a) Mean Patient-Oriented Eczema Measure (POEM) (a) averaged and (b) summed across all items in the ITT dataset.
- b) Mean score on the 30-point Infants' Dermatitis Quality of Life Index (IDQOL) summed across items in the ITT dataset

Age at onset will be tested using either pooled logistic regression or time-to-event methods for interval-censored data. For these analyses, age of onset will be indexed to the quarterly contact when the parent reported a diagnosis or to the closest corresponding age if the first diagnosis date is in the child's medical chart. Although we may not have sufficient sample size to detect an age-dependent treatment effect, it is possible that the greatest protective effects will be observed at early ages. Kaplan-Meier curves or similar visualizations may help to evaluate differences in treatment effect by age of onset.

9. Age of onset to the nearest 3 months determined by

- a) parental report of eczema from quarterly contacts or annual questionnaires
- b) provider-recorded date of first diagnosis retrieved from record review of chart by research coordinator indexed to the nearest quarter of follow-up

Mean days of disrupted sleep will be treated as a **count** variable and tested with a Poisson model similar to those described above.

10. Lower mean days of disrupted sleep in the past week for infants reported by parents at
 - a) 12 months
 - b) 24 months

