5.9. Missing Data

The approach to missing data will be guided by sources such as Jakobsen et al²¹ on missing data in randomized trials.

Definition of missingness in the primary outcome: The primary outcome, AD by 24 months of age, will be ascertained through review of medical records by research personnel blinded to intervention status and will be considered *not missing* if either (1) a diagnosis of AD is found for any visit before age 24 months (± 3 months), *or* (2) no diagnosis is found *and* the child had at least one visit in the 24-month window. The outcome will be considered missing if those conditions are not met, i.e. we

find no diagnosed AD before age 2 years *and* no clinic visit within ± 3 months of the child's second birthday.

COVID-19 pandemic as a cause of missingness: Because the primary outcome depends on an in-person clinic visit, it is likely to be missing for children who would otherwise have had visits during periods when the clinic was not offering in-person care or when parents declined to bring children for non-urgent care. The study team discussed extending the window for chart reviews to mitigate this effect, but this would require contacting parents for consent and was not adopted.

Missingness in other variables: Other variables from parent report will be considered missing if the response is absent or "don't know/unsure" or similar. In chart reviews, missingness will occur if a visit is not found, but if a visit is found, a "not found" for a particular category (e.g. medication) will be considered a non-missing "no." Validated multi-item scales will be scored according to published guidelines when available. When guidelines are not available, decisions about how to treat missing responses will be made and recorded before the dataset is locked for analysis.

If $\leq 5\%$ of observations are missing the primary outcome, then multiple imputation methods will not be of benefit and we will perform analysis without imputation. The treatment assignment, family history of atopic dermatitis, and recruiting clinic are assigned or used to create arm assignments and so will be complete for all participants.

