Table Title	Population	Time Point(s)	Endpoint	Endpoint Type	Summary Statistics by Treatment Assignment
Breathing Problems	ITT	12m,24m	Ever wheeze	Binary(Y/N)	p%(x/n)
			Number of wheeze events over past year (cat)	Count	p%(x/n)
			Wheeze without cold	Binary(Y/N)	p%(x/n)
			Diagnosed asthma	Binary(Y/N)	p%(x/n)
			Asthma predictive index-Y/N (derived)	Binary(Y/N)	p%(x/n)
Allergies	ITT	12m,24m	Skin Prick Test or Blood test	Binary(Y/N)	p%(x/n)
			Food allergy symptoms	Binary(Y/N)	p%(x/n)
			Food exposure	Binary(Y/N)	p%(x/n)
Severity of symptoms and influence on quality of life	AD population	12m,24m	POEM score (0-28)	Continuous	n, mean, SD, Median, min, max
			IDQOL score (0-30)	Continuous	n, mean, SD, Median, min, max
	ITT	12m,24m	Parent-rated health status	Ordinal(1-5)	p%(x/n) n, mean, SD, Median, min, max
			Days of disrupted sleep in the past week	Count(0-7)	p%(x/n) n, mean, SD, Median, min, max
			Adverse reaction to skin product	Binary(Y/N)	p%(x/n)
Adverse events	ITT	12m,24m	Type	Categorical	p%(x/n)
			Ended	Binary(Y/N)	p%(x/n)
			Severity	Categorical	p%(x/n)
			Require HCP visit	Binary(Y/N)	p%(x/n)
			Diagnosis	Categorical	p%(x/n)
			AE Treatment-Y/N	Binary(Y/N)	p%(x/n)
			AE Treatment-name	Categorical	p%(x/n)
			SAE listing	Narrative	n/a
					p%(x/n)
Contact info change	ITT	Any time			p%(x/n)

Table 5. Exploratory analyses

Subgroup	Intervention cumulative incidence	Usual care cumulative incidence	Difference (risk difference) 90% CI	Difference in differences	Risk Ratio 90% CI	Difference (ratio scale)	P value for interaction
Family history of atopy							
Yes							
No							
Climate							
Dry							
Wet							
Domestic animals							
Any							
None							
Cat(s)							
Dog(s)							
Farmanimal(s)							
Sex							
Female							
Male							
Age at randomization							
Youngest							
Middle							
Oldest							
Emollient type used							
CeraVe							
Others							
None							

6. References

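### The POEM rule sums five or six answered items as if they were seven, so incomplete responses can only be scored equal to or milder than the truth; the effect is small and confined to a secondary endpoint

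*SAP*

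**What the plan says.** SAP 5.1 item 9a scores each of seven POEM items as "0, No days | 1, 1-2 days | 2, 3-4 days | 3, 5-6 days | 4, Every day". The total is to be formed as follows: "calculate the sum of the seven items for any respondent who answered at least five of the component questions". A condition is attached: "if the incomplete responses are <10% of the total responses". No value is given for the unanswered items: no proration, no item imputation and no explicit zero. Nor does the SAP say what happens at 10% or more, or whether the percentage is taken overall, by arm or by time point. Table 4 in SAP 5.12 summarises POEM at 12 and 24 months on a 0 to 28 range.

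SAP 5.4 item 8a then lists two versions of the endpoint: "Mean Patient-Oriented Eczema Measure (POEM) (a) averaged and (b) summed across all items in the ITT dataset". The divisor of the average is not stated. The item refers to the ITT dataset, but its lead-in and Table 4 both place POEM in the AD population, and I read it that way.

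Two other passages bear on the point. The text that introduces the secondary hypotheses in SAP 5.1 treats don't-know answers as missing. SAP 5.9 adds: "Validated multi-item scales will be scored according to published guidelines when available".

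**The concern.** A respondent with five or six answers has no seven items to sum. The obvious way to program the rule is to add up what is present, which gives the same result as recording no days for each blank. A missing answer then becomes absence of the symptom, although the SAP elsewhere treats non-informative answers as missing. The error runs one way only.

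At stake is the comparison of symptom severity between arms among children with AD. Equal skipping shrinks both means alike. Unequal skipping creates a difference that has nothing to do with severity. Parents complete POEM and are not blinded (Protocol 4.5), so unequal skipping is possible, though nothing in the documents shows that it occurs.

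**Working it through.** **Inputs from the SAP.** Seven items, each 0 to 4; at least five answered; incomplete responses below 10% (all 5.1 item 9a); range 0 to 28 (Table 4). For the precision check, 491 per arm with AD in 24% and 16.8% (2.3).

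**Assumed, because the documents give no figure.** True POEM mean 7 to 14; share with two blanks 9% in one arm and 3% in the other; SD of POEM 4 to 7.

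**1. Reproduce the range.** 7 × 4 = 28, which agrees with Table 4.

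**2. Highest attainable score under a plain sum.** Six answered: 6 × 4 = 24. Five answered: 5 × 4 = 20.

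**3. Shortfall if blanks equal the mean of the answered items.** This is 1 − answered/7. One blank: 1/7 = 14.3%. Two blanks: 2/7 = 28.6%.

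**4. Shortfall without that assumption.** For a true total T and m blanks, the points lost lie between max(0, T − 4(7 − m)) and min(T, 4m). One blank loses 0 to 4 points and two blanks lose 0 to 8. For two blanks:

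| True total | Points lost | Share of true total |
|---|---|---|
| 8 | 0 to 8 | 0 to 100% |
| 16 | 0 to 8 | 0 to 50% |
| 24 | 4 to 8 | 17 to 33% |
| 28 | 8 | 28.6% |

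**5. Effect on the pooled mean below the 10% limit.** With two blanks each, and incomplete respondents as severe as the others: 0.10 × 2/7 = 2.9% at most. With one blank each: 0.10 × 1/7 = 1.4%. Without the proportional assumption, the limit is 0.10 × 8 = 0.8 points.

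**6. Effect on the arm comparison (illustration).** (0.09 − 0.03) × 7 × 2/7 = 0.12 points at a true mean of 7; (0.09 − 0.03) × 14 × 2/7 = 0.24 points at 14. As an extreme, suppose that all incomplete responses fell in one of two equal-sized groups, 20% against 0%, which is about 10% overall. That group's mean would be 0.20 × 2/7 = 5.7% low, or 0.4 to 0.8 points at a true mean of 7 to 14.

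**7. Set against precision.** The planning figures imply about 491 × 0.24 = 118 and 491 × 0.168 = 82 children with AD. The standard error of a difference in means is SD × √(1/118 + 1/82) = SD × 0.144, or 0.58 to 1.01 points for an SD of 4 to 7. A distortion of 0.24 points is therefore about a quarter to two-fifths of one standard error.

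**8. After proration.** The multiplier is 7/6 = 1.167 for six answers and 7/5 = 1.40 for five, and the maximum returns to 28 in both cases (24 × 7/6; 20 × 7/5).

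**The case against.** The strongest reply is that the SAP never says blanks are zero. It is silent, and SAP 5.9 sends validated scales to published guidelines. If a published POEM rule for missing items exists, it may settle the matter; that cannot be checked from these documents. This stands in part: zero-scoring is the literal consequence of the text, not a stated intention. But item 9a is the specific instruction a programmer would follow, and it does not say whether it is the published rule.

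The 10% condition also works as a safeguard, since it limits the pooled error. That stands too; what is missing is a rule for 10% or more.

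Three stronger readings are tempting, and the documents do not support them.

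- A reader might take 29% as the most an incomplete score can be low. It holds only if the two blanks resemble the answered items; step 4 shows that the error for one child can be anywhere from nothing to the whole score.
- A reader might infer that the averaged and summed versions in 5.4 contradict each other. They do so only if the average divides by items answered. Divided by seven, they agree, and both carry the same error.
- A reader might call the IDQOL rule ("A missing item will result in a missing response") an inconsistency. It is a different instrument, and SAP 5.9 allows each scale its own scoring rule.

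**Conclusion.** The point holds as a small, one-directional scoring flaw. Applied as written, the rule can only score an incomplete respondent equal to or milder than the truth. The pooled mean is at most about 2.9% low while incomplete responses stay below 10%, if blanks resemble answered items and incomplete respondents are otherwise like the rest.

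A biased arm comparison is not demonstrated. It needs skipping to differ by arm, and the 0.12 to 0.24 points rest on an assumed mean and assumed skipping rates. A shift of that size is unlikely to change a conclusion. POEM is a secondary endpoint in children with AD, so the primary analysis is untouched. The reason to act is that the change is nearly free and removes a scoring decision that would otherwise be made at the programming stage.

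**What to change.** Before the dataset is locked:

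- In SAP 5.1 item 9a, score POEM as 7 times the mean of the answered items when at least five are answered, and as missing otherwise. If a published POEM rule for missing items applies under SAP 5.9, cite it and use it instead.
- In SAP 5.4 item 8a, divide the averaged version by the number of items answered, or drop it. With that divisor it is the prorated sum divided by seven and adds no information.
- Apply the same rule whether or not incomplete responses reach 10%, and report the number of incomplete responses by arm and time point.

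The cost is a sentence or two and a line of code. There is one real downside: proration assumes that skipped items resemble answered ones, and it would over-score a child if the rarer symptoms are the ones skipped.

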2.2.2 Secondary Outcomes

- Parental report of provider-diagnosed AD - This parental report of AD question has been validated previously by our group and was found to have adequate sensitivity and specificity during our trial planning activities.³⁹

- AD as diagnosed by the Children's Eczema Questionnaire (CEQ) – The CEQ is a newly developed 2-question parental questionnaire based on the U.K. Working Party criteria.⁴⁰ This instrument will be used to capture dyads not evaluated by their provider or lost to follow-up (Appendix A).
- Parental report of sleep loss of the infant reported as average parental report of days per week of disrupted sleep in their infant (1 week recall) measured at 12 and 24 months.
- Any prescription topical medication use or over-the-counter hydrocortisone usage recorded by parent or recorded from records review by research coordinator at 24 months.
- Asthma risk questions from the modified Asthma Predictive Index (mAPI) that uses family history, atopic dermatitis, sensitization history, and wheezing episodes to predict the development of asthma measured by parental report.⁴¹ This will be recorded as either high risk or low-risk at 12 and 24 months following mAPI criteria (Appendix B). Wheezing episodes will be assessed using the International Study of Asthma and Allergies in Childhood (ISAAC) questionnaire.
- Parental report of immediate food allergy symptoms – A general question regarding the development of red rash/hives, lip swelling, wheezing, abdominal pain, or vomiting that developed in the infant within two hours of eating a food.
- Parental report of a provider diagnosis of food allergy that was confirmed by prick testing or IgE blood test.
- One question global health status from the PROMIS Pediatric Global Health (PGH-7) instrument.⁴² (Appendix C)
- In infants who develop AD, a logic model in our survey instrument will ask the following parental reported outcomes in the 12- and 24-month questionnaires:
 1. Time to onset of AD as measured by parental report of eczema age of onset.
 2. Time to onset of AD as measured by provider-recorded date of first diagnosis retrieved from record review of chart by research coordinator.
 3. AD symptom severity as reported by the Patient-Oriented Eczema Measure (POEM) instrument⁴³ (Appendix D).
 4. Parent-reported global severity of eczema assessment – mild, moderate, severe

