 5. Infant Dermatology Quality of Life Instrument (IDQOL) – a validated 10-question questionnaire designed for children under 4 years of age⁴⁴ (Appendix E).

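### SAP 5.1 item 9b scores the 30-point IDQOL by summing twelve items that reach 41; secondarily, the asthma index in item 6b, read literally, never requires wheeze

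*SAP*

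**What the plan says.** **IDQOL.** SAP 5.1 item 9b describes a 30-point index and gives the scoring rule: "To score, sum the items below. A missing item will result in a missing response". The severity item is coded "4, Extremely Severe | 3, Severe | 2, Average | 1, Fairly Good | 0, No Eczema". The nights item ends "sleep was disturbed at night, not including routine feeding? 0-7". The other ten items are coded 0 to 3.

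Elsewhere the documents say:
- Protocol 2.2.2 calls the IDQOL "a validated 10-question questionnaire designed for children under 4 years" of age.
- SAP 5.4 item 8b repeats the 30-point label and has the "Quality of Life Index (IDQOL) summed across items in the ITT dataset".
- SAP Table 4 gives the IDQOL range as 0 to 30, in the AD population. It lists "Days of disrupted sleep in the past week" on its own row, as a 0-7 count in the ITT population.
- SAP Table 3 schedules sleep loss for all infants, but the IDQOL only if AD develops.
- SAP 5.1 item 11 takes the nights outcome from what it calls the fourth IDQOL item.
- SAP 5.9 says that validated scales follow published scoring guidance where it exists.

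**Asthma index.** SAP 5.1 item 6b requires at least one of three major criteria (parental asthma or AD, inhalant sensitivity, the child's eczema) and/or at least two of three minor criteria (wheeze without a cold, allergic rhinitis, eosinophilia). The same hay-fever question is printed under inhalant sensitivity and under rhinitis. Protocol 2.2.2 lists wheezing episodes among the inputs and refers to Appendix B. SAP 5.4 item 5 words the endpoint differently, adding symptoms such as wheeze or a bronchodilator prescription.

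**The concern.** The item 9b instruction cannot produce the scale that the documents declare. A programmer who follows it would report a mean on a 0-41 scale under a 0-30 label. The score would weight sleep more heavily than the ten-item instrument does, and children would drop out for a blank on a question that is not part of the 30 points. Item 11 makes this more likely, because nights is fourth only in the twelve-item list. The SAP therefore appears to treat that list as the instrument.

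For the asthma index, the or-reading lets the child's AD alone, or parental history alone, make a child positive. An arm difference would then mainly restate the AD result, diluted by a factor fixed before randomisation, and would say little about respiratory benefit.

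**Working it through.** **1. The stated maximum.** Item maxima from the response codes in item 9b, in printed order:

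4 (severity) + 3 (itch) + 3 (mood) + 7 (nights) + 3 (time to fall asleep) + 3 (total time disturbed) + 3 (play) + 3 (family activities) + 3 (meals) + 3 (treatment) + 3 (dressing) + 3 (bath) = **41** over 12 items.

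The stated 30 is not reproduced. Variants:

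| Items summed | Maximum |
|---|---|
| All twelve | 41 |
| Severity dropped | 37 |
| Nights dropped | 34 |
| Nights rescaled to 0-3, severity kept | 37 |
| Nights rescaled to 0-3, severity dropped | 33 |
| Both dropped | 10 × 3 = 30 |

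A search of all subsets of the twelve items finds exactly one with a maximum of 30: the ten 0-3 items.

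**2. Weights.** The extra items hold (4 + 7)/41 = 11/41 = 27%. Sleep items hold (7 + 3 + 3)/41 = 32%, against (3 + 3)/30 = 20% in the ten-item score.

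**3. Missing-item rule.** The documents give no item-level blank rate. Assume that each item is blank independently with probability m. The share of scorable forms is (1 − m)^12 or (1 − m)^10:

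| m | Twelve items | Ten items |
|---|---|---|
| 1% | 88.6% | 90.4% |
| 3% | 69.4% | 73.7% |
| 5% | 54.0% | 59.9% |

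The two extra items cost about 2 to 6 percentage points.

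**4. Item 11.** With severity and nights removed, the fourth remaining item is total time of disturbed sleep (0-3). Correcting 9b alone would leave item 11 pointing to the wrong variable.

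**5. Asthma index logic.** Three major and three minor criteria give 64 patterns.
- Under and: 7 major patterns × 4 minor patterns = 28 positive. Of these, 7 × 1 = 7 have no wheeze (rhinitis plus eosinophilia with any major criterion).
- Under or: 64 − 1 × 4 = 60 positive. Of the 32 patterns without wheeze, 3 are negative, so 29 are positive.

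These count logical patterns, not children.

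**6. Size under the or-reading only.** Assumptions: parental asthma or AD in q = 20-50% of children; AD 24% versus 16.8% (the planning figures); AD risk ratio by parental history rr = 1-2; no effect on wheeze; inhalant and minor criteria ignored. With p the AD risk in an arm, the risk without parental history is p0 = p/(1 + q(rr − 1)), and the proportion positive is q + (1 − q)p0.

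| q | rr | Control | Intervention | Index RR |
|---|---|---|---|---|
| 0.2 | 1 | 0.2 + 0.8 × 0.24 = 39.2% | 0.2 + 0.8 × 0.168 = 33.4% | 0.853 |
| 0.2 | 2 | 0.2 + 0.8 × 0.20 = 36.0% | 0.2 + 0.8 × 0.14 = 31.2% | 0.867 |
| 0.5 | 1 | 0.5 + 0.5 × 0.24 = 62.0% | 0.5 + 0.5 × 0.168 = 58.4% | 0.942 |
| 0.5 | 2 | 0.5 + 0.5 × 0.16 = 58.0% | 0.5 + 0.5 × 0.112 = 55.6% | 0.959 |

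Parental history accounts for 51% (0.2/0.392) to 86% (0.5/0.58) of positive controls. Power with 491 per arm (two proportions, two-sided 0.05) is 47% in the first row and 12% in the last, against 80% for AD itself.

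**The case against.** The arithmetic is not in dispute, but several points limit its weight.

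- *The intended scale is stated repeatedly, and SAP 5.9 defers to published scoring.* A score above 30 would clash visibly with Table 4. But 5.9 is a general sentence under missing data, while 9b gives an explicit sum and its own missing-item rule, and the SAP does not say which governs. A wrong mean need not exceed 30, so the clash might not show.
- *The separate severity outcome is weak support.* Protocol 2.2.2 lists "Parent-reported global severity of eczema assessment" beside the IDQOL, but in three grades, whereas the 9b item has five levels. They may be different questions. This stands: the separate listing does not prove that the 0-4 item lies outside the IDQOL. The case rests on the 30-point label, the 0-30 range and the ten-question count.
- *Most of the missing-form loss comes from the all-or-nothing rule on ten items, which the fix keeps.* This is correct, and the blank rates are assumed.
- *The asthma point is less certain.* Appendix B is not in the text available, layout may have been lost in item 6b, and the chart-review wording leaves open whether one hay-fever answer satisfies both criteria. Under the and-reading, eczema with rhinitis and eosinophilia also qualifies, so barring double counting would not by itself make wheeze necessary. The power figures illustrate only the or-reading. Parent-reported asthma diagnosis and wheeze are already tabulated separately. All of this stands, and it is why the point is secondary and asks only for reconciliation.

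**Conclusion.** The concern holds. For the IDQOL, confidence is high: the item count (12) and maximum (41) are exact, no reading of the instruction gives 30, and the documents' own figures identify the ten-item score as the only consistent one. Following the plan as written puts a secondary severity endpoint on the wrong scale. The scorable-form range depends on assumed independent blanks of 1-5% per item.

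For the asthma index, confidence is moderate: wheeze is not required under either reading of and/or, but the documents available do not settle the intended rule. The 36-62% of controls positive, index RR of 0.85-0.96 and power of 12-47% depend on the or-reading and the assumptions listed. The primary analysis and sample size are unaffected. The SAP should be corrected.

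**What to change.** **IDQOL.** In item 9b, name the ten 0-3 items as the score (range 0-30) and apply the missing-item rule to those ten only. Report the 0-4 severity item separately, stating how it relates to the protocol's three-grade global severity outcome. Use the nights item only for outcome 11, and refer to it there by its text rather than as an IDQOL item number. Make both edits together.

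**Asthma index.** Reconcile item 6b with Protocol 2.2.2, Appendix B and SAP 5.4 item 5. State whether the link is and or or, and state explicitly whether wheeze is required. Do not let one hay-fever answer count as both a major and a minor criterion. Interpret the index beside the planned parent-reported asthma diagnosis and wheeze outcomes.

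**Cost.** SAP wording and a few lines of scoring code before database lock; all items are already collected. Depending on how item 6b is resolved, fewer children may be asthma-positive, which would lower power for that endpoint.
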